5.9.3. Data Monitoring Committee

There will be no Data Monitoring Committee used for this study.

5.10. Total Blood Volume

The total blood volume to be collected for each patient enrolling in this study is approximately 131.5 mL for scheduled tests. An additional 30 mL of blood may be collected in the event of follow-up for liver enzymes as detailed in [Appendix J](#).

Details are provided in [Appendix L](#).

6. ASSESSMENT OF EFFICACY

Data from any efficacy assessments performed after the specified time will not be collected on the CRF. However, in the event that such data are collected, these data will not be analyzed.

6.1. Electronic Diary Device

Efficacy endpoints related to CH attacks will be derived from data collected daily using an electronic diary device. Eligible patients will receive comprehensive training at screening from the investigational site personnel on the use of the electronic diary device. Investigational site personnel will also instruct patients on the requirement for timely and daily completion of the electronic diary.

Patients will complete electronic headache diary entries with questions about the previous day, starting from the day after the screening visit through the end of treatment (EOT)/early withdrawal visit. The electronic headache diary device will allow entry of headache information for up to 2 days after a given day.

Patients who report a CH attack will answer questions about the attack (ie, occurrence and number of CH attacks, duration of CH attack[s], severity of CH attack[s], and acute CH-specific medication and oxygen use). The last day of the run-in period should be reported in the morning of the visit day.

Patients will be asked about their performance at work or at school on CH attack-free days. Additional details can be found in the electronic diary device training manual.

If a patient fails to complete the diary for the preceding day, the patient will be prompted to enter the missed day's information the next time he/she accesses the electronic diary provided no more than 2 days have elapsed since completion of that day. If more than 2 days have elapsed since completion of a diary day, the patient will not be allowed to enter diary information for that day, and it will be considered a missed day.

If a CH is reported, then CH intensity will be subjectively rated by the patient as follows:

- Mild
- Moderate
- Severe
- Very severe

6.2. Hospital Anxiety and Depression Scale

The HADS is a validated and reliable, 14-item scale developed by [Zigmond and Snaith \(1983\)](#) to measure anxiety (7-items) and depression (7-items). Each item is scored on a 4-point scale from 0 to 3. Scores for depression and anxiety range from 0 to 21; a score of 0 to 7 is normal, 8 to 10 is borderline abnormal, and 11 to 21 is abnormal.

Patients will complete the HADS in the investigational site tablet at the time points detailed in [Table 2](#).

6.3. EuroQol-5 Dimension Questionnaire

The 5-level EQ-5D (EQ-5D-5L) is a standardized questionnaire that assesses overall state of health. The EQ-5D-5L consists of 2 parts. In part 1, patients rate their health state in 5 domains: mobility, self-care, usual activities, pain/discomfort, and mood using a scale of 1 to 5, where 1 = no problems, 2 = slight problems, 3 = moderate problems, 4 = severe problems, and 5 = extreme problems. In part 2, patients rate their health state on a 100 mm visual analog scale; a rating of 0 represents the worst imaginable health state, and a rating of 100 represents the best imaginable health state.

Patients will complete the EQ-5D-5L in the investigational site tablet at the time points detailed in [Table 2](#).

6.4. Twelve-Item Short-Form Health Survey

The SF-12 (version 2) is a generic health survey containing 12 questions to measure functional health and well-being rated in 8 health domains (physical function, role limitations due to physical problems, bodily pain, general health perceptions, vitality, social functioning, role limitations due to emotional problems, and mental health) with 1 or 2 questions per domain. The SF-12 was developed from the 36-Item Short-Form Health Survey ([Ware et al 1996](#)). Scores range from 0 to 100, with higher scores indicating better health status.

Patients will complete the SF-12 in the investigational site tablet at the time points detailed in [Table 2](#).

6.5. Work Productivity and Activity Impairment Questionnaire

The generic version of the WPAI questionnaire measures the overall effect of health on productivity at work and daily activities. The specific health problems version of the WPAI questionnaire allows investigators to attribute productivity and activity impairment issues to specific health conditions. After the employment status of a respondent is identified, 3 open-ended questions are asked concerning (1) hours absent from work due to health problems (or specific condition), (2) hours absent from work due to other reasons, and (3) hours actually worked. Two additional questions are included that ask about the impact of health on productivity, 1 concerning productivity at work and the other concerning daily activities outside of work. The response format of each item of the WPAI questionnaire consists of an 11-point scale ranging from 0 (no impairment) to 10 (complete impairment) ([Reilly et al 1993](#)).

Patients will complete the WPAI questionnaire in the investigational site tablet at the time points detailed in [Table 2](#).

6.6. Impact on Partner and Family Questionnaire

The partners/family members of patients participating in the study, if applicable, will complete an Impact on Partner and Family questionnaire at the time points detailed in [Table 2](#). Responses will be recorded in the investigational site tablet. The questionnaire will include questions about the impact of CH on the patient's ability to do chores, the number of days that the patient missed a family or social activity since the last assessment due to CH, and the frequency with which the patient avoids making plans for family/social activities due to CH. Partners/family members will

be asked to attend the study visit with the patient or to return to the investigational center within ± 3 days of the patient's visit if unable to appear at the same time.

6.7. Patient-Perceived Satisfactory Improvement

The PPSI was developed by [ten Klooster et al \(2006\)](#) for pain intensity and was adjusted for CH symptoms improvement. Patients will mark the level of CH-associated pain and indicate if pain is “much worse,” “moderately worse,” “slightly worse,” “unchanged,” “slightly improved,” “moderately improved,” or “much improved” compared with 4 weeks ago. PPSI will be defined as the change in pain that corresponds with a minimal rating of “slightly improved.”

The PPSI will be completed in the electronic diary device at home at week 1 and in the investigational site tablet at the time points detailed in [Table 2](#).

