
A secondary objective of this study is to further demonstrate the efficacy of fremanezumab in the prevention of ECH in adult patients.
	
The secondary efficacy endpoints to further demonstrate efficacy are:
 
 • the proportion of patients with a $\geq 50\%$ reduction from baseline (run-in period) in the weekly average number of CH attacks during the 4-week period after the first dose of the IMP, ie, based on week 0 to 4 data • the mean change from baseline (run-in period) in the number of CH attacks during the 12-week period after administration of the first dose of the IMP, ie, based on week 0 to 12 data • the mean change from baseline (run-in period) in the number of CH attacks during the 4-week period after administration of the third dose of the IMP, ie, based on week 8 to 12 data • the mean change from baseline (run-in period) in the weekly average number of days with use of cluster-specific acute headache medications (triptans and ergot compounds) during the 12-week period after administration of the first dose of the IMP, ie, based on week 0 to 12 data • the mean change from baseline (run-in period) in the weekly average number of days oxygen is used to treat ECH during the 12-week period after administration of the first dose of the IMP, ie, based on week 0 to 12 data • assessment of patient’s perceived improvement, as measured by the Patient-Perceived Satisfactory Improvement (PPSI) at 1, 4, 8, and 12 weeks after administration of the first dose of the IMP relative to baseline (day 0)

Objectives	Endpoints

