2. STUDY OBJECTIVES AND ENDPOINTS

2.1. Primary and Secondary Study Objectives and Endpoints

The primary and secondary study objectives and endpoints are as follows:

Objectives	Endpoints

The primary objective of this study is to demonstrate the efficacy of fremanezumab in the prevention of episodic cluster headache (ECH) in adult patients.
	
The primary efficacy endpoint of this study is the mean change from baseline (run-in period) in the weekly average number of cluster headache (CH) attacks during the 4-week period after administration of the first dose of the investigational medicinal product (IMP), ie, based on week 0 to 4 data.

A secondary objective of this study is to further demonstrate the efficacy of fremanezumab in the prevention of ECH in adult patients.
	
The secondary efficacy endpoints to further demonstrate efficacy are:
 
 • the proportion of patients with a $\geq 50\%$ reduction from baseline (run-in period) in the weekly average number of CH attacks during the 4-week period after the first dose of the IMP, ie, based on week 0 to 4 data • the mean change from baseline (run-in period) in the number of CH attacks during the 12-week period after administration of the first dose of the IMP, ie, based on week 0 to 12 data • the mean change from baseline (run-in period) in the number of CH attacks during the 4-week period after administration of the third dose of the IMP, ie, based on week 8 to 12 data • the mean change from baseline (run-in period) in the weekly average number of days with use of cluster-specific acute headache medications (triptans and ergot compounds) during the 12-week period after administration of the first dose of the IMP, ie, based on week 0 to 12 data • the mean change from baseline (run-in period) in the weekly average number of days oxygen is used to treat ECH during the 12-week period after administration of the first dose of the IMP, ie, based on week 0 to 12 data • assessment of patient’s perceived improvement, as measured by the Patient-Perceived Satisfactory Improvement (PPSI) at 1, 4, 8, and 12 weeks after administration of the first dose of the IMP relative to

Objectives	Endpoints
	baseline (day 0)

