The reader of this SAP is encouraged to read the study protocol for details on the conduct of this study, the operational aspects of clinical assessments, and the timing for completing the participation of a patient in this study.

The SAP is intended to be in agreement with the protocol, especially with regard to the primary and all secondary endpoints and their respective analyses. However, the SAP may contain more details regarding these particular points of interest, or other types of analyses (eg, other endpoints). When differences exist in descriptions or explanations provided in the study protocol and this SAP, the SAP prevails; the differences will be explained in the clinical study report.

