6.3.4. Mean Change from Baseline in the Weekly Average Number of Days Oxygen is Used to Treat Episodic Cluster Headaches During 12-week Period After Administration of the First Dose of the IMP

Use of oxygen will be recorded in the e-diary. The 12-week period is the period from administration of the first dose of the IMP to the EOT/early withdrawal visit. The weekly average number of days using oxygen for a patient during the 12-week period will be calculated and prorated to 7 days using formula [1]. Missing data handling method is provided in Section 6.1.4.2.

Data will be analyzed using an ANCOVA method in a manner analogous to the primary endpoint as described in Section 6.2.2.

MMRM analysis will be based on weekly analysis windows. Data in weekly analysis windows will be derived.

6.3.5. Patient-Perceived Satisfactory Improvement at 1, 4, 8, and 12 Weeks After Administration of the First Dose of the IMP Relative to Baseline

The PPSI scale will be completed in the e-diary at home at week 1 (day 7) and in the investigational site tablet at the visits 2, 3, 4, and 5. Patients will mark the level of CH-associated pain and indicate the level of pain using the following scale compared with 4 weeks ago:

- 1 = Much worse
- 2 = Moderately worse
- 3 = Slightly worse
- 4 = Unchanged
- 5 = Slightly improved
- 6 = Moderately improved
- 7 = Much improved

PPSI will be defined as change in pain that corresponds with a minimal rating of “slightly improved” (Protocol Section 6.7). For analysis purpose, a dichotomous scale of “Responder” (scales 5 to 7) or “Non-responder” (scales 1 to 4) will be derived.

The percentage of patients in dichotomous scale of “Responder” or “Non-responder” at week 1, visit 3, 4, and 5 will be analyzed using a CMH method in a manner analogous to the first secondary endpoint as described in Section 6.3.1. Missing scores will not be imputed.

Modification to SAS code in Section 6.3.1: adding a ‘by’ statement for visit.

Raw scales will be summarized using descriptive statistics. A missing category will be presented if applicable.

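### PPSI is labelled as improvement from day 0 at four time points, but the item described asks about the last 4 weeks, so as written only week 4 measures the stated quantity

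*Protocol*

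**What the plan says.** The Protocol synopsis, Protocol 2.1 and 9.5.2, and SAP 1.2 all define the last-listed secondary endpoint as perceived improvement on the PPSI "at 1, 4, 8, and 12 weeks after administration of the first dose of the IMP relative to baseline (day 0"). The heading of SAP 6.3.5 repeats the reference point: "Patient-Perceived Satisfactory Improvement at 1, 4, 8, and 12 Weeks After Administration of the First Dose of the IMP Relative to Baseline".

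The instrument is described differently. In Protocol 6.7 the seven-category rating is made "compared with 4 weeks ago. PPSI will be defined as the change in pain that corresponds with a minimal rating of" slightly improved. The text of SAP 6.3.5 agrees with that: "Patients will mark the level of CH-associated pain and indicate the level of pain using the following scale compared with 4 weeks ago". Neither section gives different wording for any time point.

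For analysis, SAP 6.3.5 splits the 1 to 7 rating into responder (5 to 7) and non-responder (1 to 4). The responder percentages "at week 1, visit 3, 4, and 5 will be analyzed using a CMH method", separately by visit. No step refers the rating back to day 0 or chains successive ratings together. SAP section 16 lists no changes from the protocol.

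**The concern.** A rating against 4 weeks earlier equals a rating against day 0 only when the assessment falls 4 weeks after day 0. If the devices carry the Protocol 6.7 wording, three of the four PPSI comparisons would be reported as improvement from baseline when they measure something else.

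Weeks 8 and 12 matter most. Protocol 5.3.1 says the high first doses are meant to give a rapid response. A patient who gets that response and keeps it has nothing new to report at week 8 or 12, and the responder rule counts that patient as a failure. A patient who improves late, including by spontaneous remission, is counted as a success. Attacks are expected to continue for at least 6 weeks after screening, that is to about day 32 to 35 or later (42 days minus a run-in of 7 to 10 days). Remission can therefore fall inside the week 8 and week 12 look-back periods.

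The synopsis places secondary endpoints under the overall type 1 error control, so these results could support formal claims.

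**Working it through.** The plan gives no figure to reproduce here. The check is where each rating points.

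**Inputs.** Protocol day numbering (first dose on day 0); PPSI at day 7 (Appendix B) and at days 28, 56 and 84, each ±3 (Table 2); look-back of 28 days (Protocol 6.7, SAP 6.3.5); screening 7 to 10 days before visit 2 (Appendix B); cycle onset 0 to 14 days before screening (inclusion criterion d).

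**Anchor day = assessment day - 28.**

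| Assessment | Anchor | With visit window | Day 0? |
|---|---|---|---|
| Week 1 | 7 - 28 = -21 | no window stated | no |
| Week 4 | 28 - 28 = 0 | -3 to 3 | yes |
| Week 8 | 56 - 28 = 28 | 25 to 31 | no |
| Week 12 | 84 - 28 = 56 | 53 to 59 | no |

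**Week 1.** With run-in length r and onset o days before screening, the cycle starts on day -(r + o). Day -21 lies in the cycle only if r + o ≥ 21. Over r = 7 to 10 and o = 0 to 14 there are 4 × 15 = 60 whole-day combinations. The numbers that qualify are 1, 2, 3 and 4 for r = 7, 8, 9 and 10, giving 10 of 60. In the other 50 (83%) the anchor precedes the cycle. These are unweighted combinations, not patients.

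**Weeks 8 and 12.** Let R(t) be the share improved since day 0 by week t, with no relapse. Let q be the share of those already improved at the anchor who still mark an improved category, the same in both arms. Then

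scored responders = R(w) - R(w-4) + q·R(w-4) = R(w) - (1-q)·R(w-4).

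With D the true between-arm difference since day 0,

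scored difference = D(w) - (1-q)·D(w-4), and share lost = (1-q)·D(w-4)/D(w).

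If the benefit is complete by week 4 and held, D(4) = D(8) = D(12) and the share lost is exactly 1 - q.

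**Illustration only.** Assume R(t) = 1 - exp(-ln2·t/median), with active versus placebo medians of 3 v 6, 4 v 8, 5 v 10 and 6 v 12 weeks. For 4 v 8 and q = 0.5, D(4), D(8) and D(12) are 20.7, 25.0 and 22.9 points. The scored differences are 25.0 - 0.5 × 20.7 = 14.6 at week 8 and 22.9 - 0.5 × 25.0 = 10.4 at week 12. Across the four pairs:

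| q | Share lost, week 8 | Share lost, week 12 |
|---|---|---|
| 1 | 0% | 0% |
| 0.9 | 7-10% | 9-13% |
| 0.75 | 18-24% | 23-32% |
| 0.5 | 35-49% | 47-64% |
| 0.25 | 53-73% | 70-96% |
| 0 | 70-97% | 93-128% |

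A loss above 100% is a reversed sign. The medians and q are assumptions, not document figures.

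**The case against.** The strongest objection is that nobody outside the sponsor can see what patients were asked. SAP Appendix A (the e-diary questionnaire, which may hold the week 1 item) is blacked out, and the tablet wording for visits 2 to 5 is not shown. What is demonstrated is a conflict of text, not a mis-measured endpoint. This stands, so every consequence here is conditional on the devices carrying the 6.7 wording. The Amendment 01 log does show the 6.7 anchor moving from day 0 to 4 weeks ago. The reason it logs concerns the visual analogue scale, however, and the conflict in the current text does not depend on the log.

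The size is also uncertain. The illustrated loss runs from nothing to reversal, it assumes the same q in both arms, and patients may go on improving between visits. That stands too: sustained benefit may be under-counted, by an unknown amount.

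There is mitigation. Raw ratings are summarised, so a drift to the unchanged category would be visible. The Patient Global Impression of Change is anchored to the start of the study, and other secondary endpoints measure attack counts from baseline. None of this alters the PPSI responder rule that is tested. Both descriptions also have patients mark a pain level. If a level is stored at visit 2, a day 0 comparison could be built, but SAP 6.3.5 derives the responder from the rating alone.

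Two ways of reconciling the texts fail. The precedence clause ("When differences exist in descriptions or explanations provided in the study protocol and this SAP, the SAP prevails") cannot settle a conflict that lies inside SAP 6.3.5 itself. Reading 4 weeks ago as loose wording for baseline sits badly with the explicit start-of-study anchor in Protocol 6.8. It also sits badly with the PPSI being completed before dosing at visit 2, where a rating of change since day 0 would mean nothing.

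**Conclusion.** The concern holds as stated. The endpoint label and the item have different reference points at weeks 1, 8 and 12, and they agree only at week 4, to within the 3-day visit window. Confidence is high on the conflict and moderate on its consequence, because the fielded wording is unseen.

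If the item reads as in Protocol 6.7, three of the four PPSI results do not support a from-baseline statement, and an early, lasting benefit may be under-counted at weeks 8 and 12. Each between-arm test remains valid under no effect. The primary endpoint, the sample size and the other secondary endpoints are not affected. The point is worth fixing because PPSI is a prespecified secondary endpoint and the anchor decides what may be claimed from it.

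**What to change.** Before unblinding:

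1. Confirm the PPSI wording actually fielded on the e-diary (week 1) and on the site tablet (visits 2 to 5).
2. If it is anchored to the start of treatment, correct Protocol 6.7 and SAP 6.3.5 and keep all four time points.
3. If it asks about 4 weeks ago, restrict the day 0 label and claim to week 4. Relabel weeks 1, 8 and 12 as change versus 4 weeks earlier in the Protocol synopsis, 2.1 and 9.5.2 and in SAP 1.2 and 6.3.5. Whether those three are still formally tested is the sponsor's choice.
4. If the two devices differ, state the anchor for each time point separately.

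The cost is a wording check on two devices and a dated text change to a prespecified secondary endpoint, with no new patients or data. The downside is that under step 3 three time points no longer support a from-baseline claim. A choice of anchor made after unblinding would look driven by the results.

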6.8. Patient Global Impression of Change Scale

The PGIC scale is a validated generic tool for the assessment of overall change in the severity of illness following treatment. Patients will rate the change in their overall health and well-being compared with how they felt at the start of the study (the time after the patient received the first IMP dose) as “much worse,” “moderately worse,” “slightly worse,” “stayed the same,” “a little better,” “moderately better,” or “much better.”

Patients will record responses to the PGIC scale in the electronic diary device at home at week 1 and in the investigational site tablet at the time points detailed in [Table 2](#).

7. ASSESSMENT OF SAFETY

In this study, safety will be assessed by qualified study personnel by evaluating reported adverse events, clinical laboratory test results, vital signs measurements, ECG findings, physical examination findings (including body weight measurements), injection site reaction/pain assessments, eC-SSRS scores, and use of concomitant medication.

7.1. Adverse Events

7.1.1. Definition of an Adverse Event

Any untoward medical occurrence in a patient or clinical investigation subject administered a pharmaceutical product and which does not necessarily have to have a causal relationship with this treatment.

An adverse event can, therefore, be any unfavorable and unintended physical sign, symptom, or laboratory parameter that develops or worsens in severity during the course of this study, or significant worsening of the disease under study, or of any concurrent disease, whether or not considered related to fremanezumab. A new condition or the worsening of a pre-existing condition will be considered an adverse event. Stable chronic conditions (such as arthritis) that are present before study entry and do not worsen during this study will not be considered adverse events.

Accordingly, an adverse event can include any of the following:

- intercurrent illnesses
- physical injuries
- events possibly related to concomitant medication
- significant worsening (change in nature, severity, or frequency) of the disease under study or other pre-existing conditions
- drug interactions
- events occurring during diagnostic procedures or during any washout phase of this study
- laboratory or diagnostic test abnormalities that result in the withdrawal of the patient from the study, are associated with clinical signs and symptoms or a serious adverse event, require medical treatment or further diagnostic work-up, or are considered by the investigator to be clinically significant.

(Note: Abnormal laboratory test results at the screening visit that preclude a patient from entering the study or receiving study treatment are not considered adverse events.)

Medical occurrences that begin before dosing of the IMP but after obtaining informed consent will be recorded on the Medical History/Current Medical Conditions section of the CRF.

